6.1 Inclusion criteria

1. Provided written informed consent
2. Aged 45 years and older
3. Previous history of chronic HF
4. HF decompensation within 6 months prior to randomization, defined as hospitalization for HF or IV diuretic treatment for HF without hospitalization.

5. NT-proBNP ≥ 300 or BNP ≥ 100 pg/mL in sinus rhythm, or NT-proBNP ≥ 600 or BNP ≥ 200 pg/mL in atrial fibrillation within 30 days prior to randomization.
The most appropriate natriuretic peptide level cut-off should be guided by the investigator's judgment of the impact of the heart rhythm at the time of blood draw on natriuretic peptide levels.
6. Diagnostic criteria of HFpEF by echocardiography assessed within 12 months prior to randomization (most recent measurement must be used to determine eligibility with no interim event signaling potential deterioration in ejection fraction)
 - o LVEF $\geq 45\%$ **and**
 - o Structural changes indicated by at least one of the following parameters:
 - LV hypertrophy (any of the following: intraventricular septal or posterior wall thickness ≥ 1.1 cm, and/or LV mass index ≥ 115 g/m² in male and ≥ 95 g/m² in female), **or**
 - LA enlargement (any of the following: LAV index ≥ 29 ml/m², or LAV >58 mL in male and >52 mL in female patients, or LA area >20 cm², or LA diameter >40 mm in male and >38 mm in female patients)
7. NYHA class II or III at randomization
8. Men or women
 - o Women of childbearing potential can only be included in the study if a pregnancy test is negative and if they agree to use acceptable effective contraception when sexually active. This applies for the time period between signing of the informed consent form and time point after the last administration of study drug. The definition of acceptable effective contraception will be based on the judgment of the investigator and on local requirements.
 - o Women are considered post-menopausal and/or not of childbearing potential if they have had 12 months of natural (spontaneous) amenorrhea with an appropriate clinical profile (e.g. age appropriate, history of vasomotor symptoms) or 6 months of spontaneous amenorrhea with serum FSH levels >40 mIU/mL [for US only: and estradiol <20 pg/mL] or have had surgical treatment such as bilateral tubal ligation, bilateral ovariectomy, or hysterectomy

6.2 Exclusion criteria

1. Clinical instability at randomization, defined by any of the following:
 - o Any IV treatment including IV diuretics or IV fluids within 24h prior to randomization
 - o SBP ≥ 160 mmHg
 - o SBP <110 mmHg and/or DBP <40 mmHg and/or symptomatic hypotension
 - o Resting HR <50 or ≥ 100 bpm
2. Use of IV inotropes at any time between qualifying HF event and randomization
3. Previous diagnosis of reduced EF (EF $<40\%$)

4. Hypertrophic obstructive cardiomyopathy, acute myocarditis, amyloidosis, cardiac sarcoidosis, or constrictive pericarditis
5. Primary valvular heart disease requiring surgery or intervention, or within 3 months after valvular surgery or intervention, or active endocarditis
6. Acute coronary syndrome (unstable angina, NSTEMI or STEMI) or PCI or CABG within 60 days prior to randomization, or indication for PCI or CABG at the time of randomization
7. Symptomatic carotid stenosis, or TIA or stroke within 60 days prior to randomization
8. Complex congenital heart disease
9. Non-cardiac comorbidity (any of the following)
 - eGFR <30 ml/min/1.73 m² calculated by MDRD formula
 - Hepatic insufficiency classified as Child-Pugh B or C
 - Morbid obesity with a BMI >45 kg/m²
 - Malignancy or other non-cardiac condition limiting life expectancy to <1 year, per physician judgment
 - Requires continuous home oxygen for severe pulmonary disease or has interstitial lung disease
 - Patients with allergies, intolerance or hypersensitivity to the investigational drug or any of the excipients
 - Medical, psychiatric, or other condition or history thereof that in the opinion of the investigator would impair the ability to complete the planned study procedures
10. Concurrent or anticipated use of PDE5 inhibitors
11. Concurrent or anticipated use of an sGC stimulator
12. Concurrent or anticipated use of long-acting and short -acting nitrates or NO donors for any route, including isosorbide dinitrate, isosorbide 5-mononitrate, pentaerythritol tetranitrate, nicorandil, NTG and molsidomine
13. Previous (within 30 days of randomization) or concomitant participation in another clinical study with investigational medicinal product(s)
14. Close affiliation with the investigational site; e.g., a close relative of the investigator, dependent person (e.g., employee or student of the investigational site)
15. Previous assignment to treatment during this study to prevent randomizing patients twice
16. Illiteracy and /or inability to read the questionnaire for any reason, as the primary endpoint is based on data collected from a self-administered patient-reported questionnaire
17. Patients who are non-ambulatory or in the view of the investigator are not able to perform a 6MWT. For ATS Statement: Guidelines for the 6MWT see Section 16.1).
18. Pregnancy or lactation
19. Previous use of vericiguat
20. Known current alcohol and/or illicit drug abuse that may interfere with the patient's safety and / or compliance at the discretion of the investigator

6.3 Withdrawal of patients from study

6.3.1 Withdrawal

Withdrawal from study

Unnecessary withdrawal of patients from the study follow-up should be avoided and all efforts should be taken to motivate patients to adhere to all study procedures and to be followed until the end of the trial.

The investigator should explore all possible options to reach a patient who fails to return to a visit or to respond to the site contact attempts. The site must document all attempts to try to contact the patient in the medical records / source documents. In order to avoid loss-to-follow-up, the investigator should ask the patient at the study start for the contact details of a relative or friend who can be contacted in case the patient cannot be reached. Patients should not be withdrawn from follow-up unless the patient explicitly withdraws consent to be contacted. All efforts should therefore be made to discuss solutions with the patient that would enable the patient to continue with follow-up in order to minimize the number of patients who withdraw such consent. The vital status will be collected for all randomized patients who have not specifically withdrawn consent for further study follow-up by any method (telephone call, email etc.), irrespective of completion of study procedures.

Withdrawal from study drug treatment

Withdrawal from study drug treatment does not represent withdrawal from the study. As certain data on clinical events beyond study treatment discontinuation may be important to the study, they must be collected through the participant's last scheduled follow-up, even if the participant has discontinued study treatment. Therefore, all participants who discontinue study treatment prior to completion of the protocol-specified treatment period will still continue to participate in the study.

Before permanently discontinuing study drug treatment (either initiated by the patient or the investigator) a temporary interruption should be considered. Patients who have temporarily discontinued from study drug treatment should resume in line with the temporary interruption rules as soon as medically justified in the opinion of the investigator (see Section 7.4). In addition, patients should not be discontinued from the study drug or withdrawn from the study solely for reaching a potential cardiovascular event.

If permanent discontinuation of study drug treatment becomes necessary due to intolerance even at the lowest dose step or any other reason, this does not mean that the patient has withdrawn from the study follow-up. Participants may be allowed to begin study treatment again if deemed medically appropriate, unless the participant's treatment assignment has been unblinded by the investigator/delegate and/or non-study treating physician.

For participants who are discontinued from study treatment but continue to be monitored in the study, all visits and procedures, as outlined in the schedule of assessments, should be completed. If the patient is unable to attend scheduled study visits, follow-up of clinical events specified as exploratory endpoints may continue by phone, unless the patient explicitly withdraws his/her consent to any type of follow-up.

Withdrawal criteria

Patients *must* be withdrawn from the **study drug**, while all efforts should be made to continue all protocol procedures also upon study drug discontinuation, if any of the following occurs:

- In case of pregnancy or breastfeeding.
- If the investigator believes that for safety reasons (i.e., adverse event) it is in the best interest of the subject to stop study drug even at the lowest dose.

Patients *may* be withdrawn from the **study drug** if any of the following occurs:

- If a significant violation of the protocol occurs, as defined by the sponsor and the coordinating investigator.
- If the randomization code is broken via IxRS.

Patients *must* be withdrawn from the **study** if any of the following occurs:

- At their own request; at any time during the study and without giving reasons, a patient may decline to participate further. The patient will not suffer any disadvantage as a result.

Patients *may* be withdrawn from the **study** if any of the following occurs:

- If, in the investigator's opinion, continuation of the study would be harmful to the patient's well-being.
- At the specific request of the sponsor and in liaison with the investigator (e.g., obvious non-compliance, safety concerns).

Depending on the time point of withdrawal, a withdrawn patient is referred to as either "screening failure" or "dropout" as specified below:

Screening failure

A patient who, for any reason (e.g. failure to satisfy the selection criteria), terminates the study before the time point used for the definition of "dropout" (see below) is regarded a "screening failure".

Re-starting the defined set of screening procedures to enable the "screening failure" patient's participation at a later time point is not allowed – with the following exceptions:

- The patient had successfully passed the screening procedures, but could not be randomized to start subsequent treatment on schedule.
- Initial screening occurred too early to complete the required washout period after prior therapy.
- The in- / exclusion criteria preventing the patient's initial attempt to participate have been changed (via protocol amendment).

In any case, the investigator has to ensure that the repeated screening procedures do not expose the patient to an unjustifiable health risk. Also, for re-screening, the patient has to resign the informed consent form, even if it was not changed after the patient's previous screening.

Dropout

A patient who discontinues study participation prematurely for any reason is defined as a “dropout” if the patient has already been randomized.

General procedures

In all cases, the reason for discontinuation from the study drug and / or withdrawal from the study must be recorded in the CRF and in the patient's medical records.

The patient may object to the generation and processing of post-withdrawal data as specified in Section [13.4](#).

Any patient removed from the trial will remain under medical supervision until discharge or transfer is medically acceptable.

Details for the premature termination of the study as a whole (or components thereof) are provided in Section [12](#).

Patients may be allowed to begin treatment again if deemed medically appropriate, unless he/she has been unblinded.

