9.2.9 Visit 9 End of treatment – Day 168±7 (week 24)

Patients need to come to site without taking the morning dose of the study drug (this applies only for the study drug. All other medications shall be taken as scheduled).

The end of treatment visit should be scheduled at Day 168±7 also in case of premature discontinuation of study drug. All other visits and procedures should continue also if the study drug has been permanently discontinued.

- KCCQ, EQ-5D-5L, PGIC/S (see Section [9.4](#))
- Frailty assessment based on the Fried score
- Assessment of NYHA class
- Concomitant medications (see Section [8.1](#))
- Adverse events (see Section [9.6.1](#))
- Only for patients participating in the optional accelerometry substudy: Activity tracking devices are planned to be collected (see accelerometry manual).
- Physical examination
- Vital signs in sitting position (BP and pulse rate). See Section [9.7.5](#).
- 6MWT
- 12-lead ECG in patients not eligible for PK/QT assessment, see Section [9.7.4](#)
- Only in patients eligible for PK/QT assessment (all patients assessed as eligible based on the baseline ECG, see Section [9.7.4](#)) – ECG and PK sample should be collected time-matched, first ECG, subsequently PK sample:
 - 12-lead ECG (to be performed just before the PK sample is taken) to be taken prior to study drug intake (exact collection time must be documented)
 - Blood sample for PK prior to study drug intake (exact collection time to be documented)
- Central lab blood samples for NT-proBNP, hematology, clinical chemistry, coagulation and biomarkers [9.7.1](#) and blood sample for PK prior to study drug intake (exact collection time to be documented) in all patients, see Section [9.7.4](#)

- Drug accountability, incl. exact time of last dose intake the day before, and collect unused study drug
- Patient to take study drug (exact time of intake must be documented)
- Only in patients eligible for PK/QT assessment (all patients assessed as eligible based on the baseline ECG, see Section 9.7.4) – ECG and PK sample should be collected time-matched, first ECG, subsequently PK sample:
 - 12-lead ECG (to be performed just before the PK sample is taken) to be taken 1-2 h after study drug intake, exact collection times must be documented)
 - Blood sample for PK 1-2 h after study drug intake, exact collection time must be documented)

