10.3 Variables and planned statistical analyses

10.3.1 Efficacy variables

Primary efficacy variable: The primary endpoint will be change in KCCQ PLS from baseline to week 24.

The estimand of interest is the de facto or treatment policy estimand.

Population: Defined through appropriate inclusion/exclusion criteria (see Section 6.1 and 6.2) to reflect the targeted patient population.

Variable: Change from baseline in KCCQ PLS from baseline to Week 24.

Measurement of intervention effect: Regardless of stopping study treatment or adherence to study treatment.

Summary measure: Difference of LS means at Week 24.

The analysis will include all assessments post-baseline. Graphical method of Maurer and Bretz (33) will be applied for multiplicity control. The two primary hypotheses will be tested with an equally splitted two sided alpha level of 0.025.

The primary analysis of the primary endpoint will be performed using a MMRM, including treatment group (vericiguat versus placebo), study visit as fixed effects, patient as a random effect, interaction between study visit and treatment group, and adjustment for the baseline PLS values as covariates. The model will assume an unstructured covariance matrix for within-patient variability.

The analysis will be performed in the Full Analysis Set. For patients who drop out of the study, a pattern-mixture model with control-based pattern imputation will be implemented. After the patient drops out from the study, it is assumed that patients from the vericiguat arm

will show the same future trend as those on the placebo arm. Patients that discontinue from the placebo arm are assumed to evolve in the same way as placebo patients that remain in the study. For those patients who had died during the study, they will be imputed with the worst case outcome, i.e., a zero score for missing KCCQ PLS.

The model statement is:

$$Y_{ijklm} = \mu + \beta x_i + t_k + r_l + h_m + v_j + (tv)_{jk} + s_i + \varepsilon_{ij}$$

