A 5 point improvement in KCCQ OSS in patients with HFrEF is considered to represent a clinically significant change in heart failure status (35). Similarly, a change of +6.4 and -5.1 points in KCCQ PLS were associated with either small improvements or small deteriorations in clinical status, as determined by a cardiologist, in the Cardiovascular Outcomes Research Consortium study cohort in patients with HFrEF (35, 36). In addition, baseline KCCQ PLS score has also been associated with peak VO₂ and distance traveled on the 6 minute walk test (6 MWT), with 6.4 and 7.5 point differences in PLS being associated with 1SD changes for peak VO₂ and 6 MWT respectively (37). Furthermore, both anchor-based and distribution-based analyses of the SOCRATES-PRESERVED data support an improvement of 5 points in KCCQ PLS as MCID. This effect size has been proposed to the US FDA during a Type C meeting and was considered preliminarily acceptable pending additional data analyses (see Section 10.5) per Agency correspondence following the meeting. As such, this study will be powered to detect a placebo-corrected change of at least 5 point improvement in KCCQ PLS from baseline to 24 weeks. An SD of 21 points was assumed based on studies in which KCCQ PLS has been reported in the literature (38-43). The patients will also be followed until the end of the study regardless of stopping study treatment or not, hence the drop-out rate is considered negligible. Based on these considerations, the total sample size will be N=735 with N=245 each in the placebo, 10 mg vericiguat arm and 15 mg vericiguat arm in a 1:1:1 randomization.

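### Protocol 6.3.1 permits withdrawal from the study at the sponsor's request for non-compliance, which conflicts with its consent-only follow-up rule and with a treatment-policy estimand that disregards adherence

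*Protocol*

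**What the plan says.** Protocol 6.3.1 separates leaving study drug from leaving the study: "Withdrawal from study drug treatment does not represent withdrawal from the study". Patients off drug are to complete the scheduled visits (Protocol 6.3.1), and Protocol 9.2.9 repeats this at week 24: "All other visits and procedures should continue also if the study drug has been permanently discontinued". On follow-up, Protocol 6.3.1 states: "Patients should not be withdrawn from follow-up unless the patient explicitly withdraws consent to be contacted". SAP section 3 carries the same sentence, with no exception.

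The criteria lists later in Protocol 6.3.1 add a route that this sentence does not allow for. The study-level list opens "Patients *may* be withdrawn from the study if any of the following occurs", and its second item reads "At the specific request of the sponsor and in liaison with the investigator (e.g., obvious non-compliance, safety concerns". A separate study-drug list already covers significant protocol violations.

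For the primary endpoint, Protocol 10.3.1 states: "The estimand of interest is the de facto or treatment policy estimand". It adds: "Measurement of intervention effect: Regardless of stopping study treatment or adherence to study treatment". SAP 6.2.3.1 and 6.2.4 apply the same approach to KCCQ PLS and to the 6MWT. A randomized patient who leaves the study early counts as a dropout (Protocol 6.3.1) and is not replaced (Protocol 6.3.2). Missing scores are filled by control-based imputation (Protocol 10.3.1; SAP 6.2.3.1 and Appendix 9.1). Protocol 10.4 reasons that patients are followed whether or not they stop treatment, "hence the drop-out rate is considered negligible".

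**The concern.** Non-adherence is one of the events that the estimand says to disregard, so a non-compliant patient's week-24 score is part of the quantity being estimated. A rule that allows non-compliance to end study participation works against that. It can turn a score that could have been observed into one supplied by a model fitted to placebo data only.

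Non-compliance arises after randomization and may depend on treatment, through tolerability or perceived lack of benefit. The patients affected are therefore not a random subset. The error can go either way. If some benefit would have persisted, the placebo-based values understate it. If these patients would have done worse than the placebo-based values, the vericiguat arm looks better than it should.

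**Working it through.** **The passages side by side**

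| Question | General rule | Study-level withdrawal list |
|---|---|---|
| What may end follow-up? | Patient's withdrawal of consent only (Protocol 6.3.1; SAP section 3) | Also a sponsor request in liaison with the investigator (Protocol 6.3.1) |
| Does non-adherence matter to the estimand? | No (Protocol 10.3.1; SAP 6.2.3.1, 6.2.4) | It is given as an example reason to end participation |
| Are visits continued off drug? | Yes, including week 24 (Protocol 6.3.1, 9.2.9) | Not for a patient withdrawn from the study |

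The level is not in doubt, because study drug and study have separate lists. The item before this one (the investigator judges continuation harmful) also departs from the literal consent-only sentence.

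**The plan's power.** Inputs from Protocol 10.3.1 and 10.4: 245 per arm, difference 5 points, SD 21, two-sided alpha 0.025 per comparison (critical value 2.241), no allowance for drop-out.

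- SE = 21 × √(2/245) = 1.897.
- Single dose: Φ(5/1.897 − 2.241) = 65.3% (stated 65%).
- At least one dose: 1 − P(both Z below 2.241), bivariate normal, each with mean 5/1.897 and correlation 0.5 from the shared placebo arm = 80.6% (stated 80%).

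Both stated figures reproduce. The at-least-one figure has 0.6 percentage points to spare.

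**Worst-case illustration.** Assumptions, none from the documents: a share w of each vericiguat arm is withdrawn under this clause, the 5-point effect would have persisted in them, and the imputation gives them an effect of zero. The expected difference is 5 × (1 − w), with n kept at 245.

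| w | Difference | Single-dose power | At-least-one power |
|---|---|---|---|
| 0 | 5.00 | 65.3% | 80.6% |
| 2% | 4.90 | 63.3% | 79.0% |
| 5% | 4.75 | 60.3% | 76.4% |
| 10% | 4.50 | 55.2% | 71.7% |

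**Why this is an upper limit for that scenario.** The code in SAP Appendix 9.1 regresses each visit on the patient's own earlier scores, so benefit already observed partly carries into the imputed values. If 40% to 70% carried forward (an assumption), 5% withdrawal would give a difference between 5 × (1 − 0.05 × 0.6) = 4.85 and 5 × (1 − 0.05 × 0.3) = 4.93. Single-dose power would then be about 62% to 64%, not 60.3%.

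**The case against.** The strongest reply is that the clause is a narrow reserve power. It is permissive and needs both a specific sponsor request and liaison with the investigator. Protocol 6.3.1 asks that unnecessary withdrawal be avoided, which implies that some withdrawals are necessary. The consent sentence says should, in a paragraph about loss to follow-up. Obvious non-compliance is not defined. If it means failing to attend visits or complete questionnaires, no obtainable week-24 score is lost.

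Much of this stands, and it limits the point. A reader might infer that a site can drop non-compliant patients on its own, or that off-drug week-24 scores are lost as a matter of course. The documents support neither: a site cannot use the clause alone, and patients who merely stop drug are expressly kept in follow-up. A reader might also infer that the negligible drop-out assumption is wrong. An optional clause of unknown use does not show that, and Protocol 11.4 likewise expects few missing data.

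Other safeguards exist but do not recover the values at issue:

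- Vital status (Protocol 6.3.1, 9.2.10) is neither a KCCQ PLS score nor a walk distance.
- The premature discontinuation visit collects both measures (Protocol 9.2.11), and consent covers it after withdrawal (Protocol 13.4). For KCCQ it supplies a week-24 value only if it falls on Days 147 to 181 (SAP Table 4-1).
- The tipping-point and missing-at-random analyses (SAP 6.2.3.2) test sensitivity to missing scores and do not restore them.

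Reading the criteria list as exceptions to a general aim is possible, but neither document says so, and the SAP repeats the rule without the exception.

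**Conclusion.** The point holds as an inconsistency that should be corrected. Protocol 6.3.1 permits study-level withdrawal for a reason that its own follow-up rule excludes and that the estimand says to disregard. When the clause is used for a consenting patient who could still be assessed, imputation replaces observable KCCQ PLS and 6MWT data.

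The conclusion rests on the text and not on a rate. The power figures assume 2% to 10% withdrawal, full persistence of the 5-point effect and zero imputed effect. They show scale only and overstate the loss under the planned imputation. The direction of any bias in the treatment difference cannot be settled from the documents.

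**What to change.** In the Protocol 6.3.1 list of reasons for which a patient may be withdrawn from the study, remove non-compliance as a ground for ending follow-up. State that scheduled collection, in particular KCCQ and 6MWT at week 24, continues for such patients unless they withdraw consent. Then reconcile that list with the consent-only sentence in Protocol 6.3.1 and SAP section 3.

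The change concerns follow-up and data collection only. Rules on stopping study drug and on safety-based withdrawal remain with the sponsor; the safety-based items need only be made consistent with the consent-only sentence.

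Non-compliance can still be examined through the per-protocol set, which already excludes compliance below 80% or above 120% (SAP 5.1.6). The cost is a wording change and a few more visits by non-compliant patients, which the protocol already asks of patients off drug.
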